# 7.5 Multiplicity considerations

All analyses in this SAP will be carried out with a two sided 5% significance level.

Secondary analyses are considered to be exploratory and so no adjustment will be made for multiplicity.

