#### **6 STUDY OBJECTIVES**

#### 6.1 Primary Objective

The primary objective is to determine whether applying a new moisturizing cream (the test cream) for 4 weeks is superior in terms of skin barrier strengthening, when compared with (1) no treatment and (2) two reference creams in adults with a predisposition to a skin barrier defect.

- TEWL after induction of skin irritation
- Redness after induction of skin irritation

The hypotheses for the study are provided below in order of importance:

- a) Skin irritation, indicated by elevated TEWL and redness, will be reduced following treatment with the test cream compared to the untreated control.
- b) Skin irritation, indicated by elevated TEWL and redness, will be reduced following treatment with the test cream compared to the reference creams, Miniderm 20% cream and Diprobase cream.

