# 2.3 Sample size:

The sample size for this study is based on the primary end point, change in Trans Epidermal Water Loss (TEWL) after induction of skin irritation (change from day 29 to day 31), with the primary comparison being between the test treatment and no treatment and the secondary comparison being between the test treatment and the two reference treatments.

In a similar study the standard deviation of the difference in change in TEWL after induction of skin irritation was seen to be approximately 8 g/mÇ.h when comparing the no treatment group to an active treatment. (that is: standard deviation of {[Change after skin irritation in no treatment area]-[Change after skin irritation in active treatment area]}).

When comparing the difference between the test treatment and one of the two reference treatments the standard deviation was approximately 3.

If the assumptions of a paired t-test are found to be valid, for a sample of 40 participants this analysis would have >90% power to detect a difference (in change) of 3.5 g/mÇ.h between test treatment and no treatment. The same sample size would also have >90% power to detect a difference (in change) of 2 g/mÇ.h between test treatment and active treatment. If a parametric analysis is indicated then an analysis which includes the baseline as a covariate will be considered which, if there is variation at baseline may increase the power of the analysis further.

If the assumptions of a paired t-test are not met (and a suitable transformation cannot be found) then a sign test (or a wilcoxon matched pairs test) may be used. A power calculation

can be carried out for the sign test although this too makes some assumptions. This calculation shows that a sample size of N=40 would have >80% power to detect a difference such that the probability of X>0 (where X is the difference in change, as above) is approximately 0.7. This probability is not unrealistic given the data seen previously, and, if the clinically relevant difference detailed above is seen, the probability of X>0 may in fact be increased leading to higher power.

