# 4. Analysis Objectives:

# 4.1 Primary objective:

The primary objective is to determine whether applying a new moisturizing cream (the test cream) for 4 weeks is superior in terms of skin barrier strengthening, when compared with (1) no treatment and (2) two reference creams in adults with a predisposition to a skin barrier defect.

The hypotheses for the study are provided below in order of importance:

- a) Skin irritation, indicated by elevated TEWL and redness, will be reduced following treatment with the test cream compared to the untreated control.
- b) Skin irritation, indicated by elevated TEWL and redness, will be reduced following treatment with the test cream compared to the reference creams, Miniderm 20% cream and Diprobase cream.

<sup>1 Sample Size Determination for Some Common Nonparametric Tests Gottfried E. Noether Journal of the American Statistical Association, Vol. 82, No. 398. (Jun., 1987), pp. 645-647

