# 7.1 Primary Analysis

The primary analyses will compare the test treatment to no treatment and to the two reference creams in terms of change in TEWL and redness (visual scoring and mexameter) between days 31 and 29. This will be done using Analysis of Covariance (ANCOVA) with change (Day 31 - Day 29) as the outcome, treatment as a factor, subject as a random effect and day 29 incuded as a covariate. Key group comparisons (Miniderm Novum Vs Control, Miniderm Novum Vs Miniderm 20% and Miniderm Novum Vs Diprobase) will be calculated directly from the ANCOVA model.

These analyses will be carried out on both the FAS and the PPS, the analysis on the PPS will be considered supportive of the primary analysis carried out on the FAS.

In both analyses, if the assumptions of the test are not met, transformations of the raw data or alternative tests will be considered, such as the Wilcoxon matched pairs or sign test, and the most appropriate solution applied.

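### SAP 7.1 makes nine comparisons primary, each at two-sided 5%, and the plan never says which result carries the superiority claim, although its own text points to TEWL versus no treatment

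*SAP*

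**What the plan says.** SAP 7.1 compares the test cream with no treatment and the "two reference creams in terms of change in TEWL and redness (visual scoring and mexameter" readings, Day 31 minus Day 29. One ANCOVA with a random subject effect is used, and of the contrasts it says "Miniderm Novum Vs Miniderm 20% and Miniderm Novum Vs Diprobase) will be calculated directly from the ANCOVA model". The FAS is primary and the PPS supportive.

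SAP 7.5 has two sentences: "All analyses in this SAP will be carried out with a two sided 5% significance level", and "Secondary analyses are considered to be exploratory and so no adjustment will be made for multiplicity". Neither addresses multiplicity among the primary tests.

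The plan does rank its aims. Protocol 6.1 and SAP 4.1 introduce the hypotheses with "The hypotheses for the study are provided below in order of importance". Hypothesis (a) reads "Skin irritation, indicated by elevated TEWL and redness, will be reduced following treatment with the test cream compared to the untreated control", and (b) says the same of the two reference creams. SAP 2.3 describes "the primary comparison being between the test treatment and no treatment and the secondary comparison being" test cream versus the references, on TEWL. The protocol synopsis gives power only for TEWL versus no treatment, and Protocol 11.5 defines a protective effect as lower post-irritation TEWL than in the untreated area.

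The redness list differs between documents. Protocol 11.2.1 includes the 2D erythema index among the techniques for the primary redness outcome; SAP 6.4 labels that index secondary.

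**The concern.** A ranking of hypotheses is not a testing rule. Nothing says that (b) is tested only if (a) succeeds, that TEWL leads redness, or how many of the nine results must be significant for the primary objective to be met. The comparisons are all prespecified, so what is open is their interpretation. If the report used a looser reading than the plan appears to intend, 5% would no longer describe the risk of a false superiority claim.

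A testing order also keeps its level only if each step is a valid 5% test. SAP 7.1 takes all contrasts from one model with, as written, a common error variance, while the planning SDs differ by a factor of more than two.

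**Working it through.** 1. **Count.** 3 measures × 3 comparators = 9 FAS tests. Two-sided 5% gives each a 2.5% chance of a false result in favour of the test cream.

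2. **The plan's own power figure.** SAP 2.3 states more than 90% power for a difference of 3.5 at N=40, where the "standard deviation of the difference in change in TEWL after induction of skin irritation was seen to be approximately 8" g/m²/h. Paired t-test, two-sided 5%: noncentrality 3.5 × √40 / 8 = 2.77, so power is 77.0%, not above 90%. At N=50 (Protocol 13.2): 3.5 × √50 / 8 = 3.09, power 85.8%. Against a reference (2, SD 3, N=40): 2 × √40 / 3 = 4.22, power 98.4%, which agrees with the plan. These figures matter here only for the cost of the fix.

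3. **Chance of at least one false favourable result.** Multivariate-normal simulation, 400,000 draws, threshold z > 1.96. Contrasts within a measure share the test-cream site (equal variances); each test is taken at its nominal size. The documents give no between-measure correlation r, so it is assumed.

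| Reading | r=0 | 0.3 | 0.5 | 0.7 | 0.9 |
|---|---|---|---|---|---|
| Only TEWL vs no treatment counts, or all must succeed | at most 2.5% | same | same | same | same |
| Any of the three no-treatment tests may win; all three null | 7.4% | 6.9% | 6.2% | 5.4% | 4.2% |
| Any of nine may win; only the six reference nulls true | 13.0% | 12.1% | 11.0% | 9.7% | 7.5% |
| Any of nine may win; all nine null | 17.7% | 16.3% | 14.8% | 13.0% | 10.2% |

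Check for three independent tests: 1 − 0.975³ = 7.3%. With SDs of 8, 3 and 3 in place of equal variances, the last row becomes 19.0% to 11.1%.

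4. **Common error variance.** In the pooled model without the covariate, the variance of a difference between two sites is the mean of the six squared pairwise SDs. Known: test vs untreated 8, test vs one reference 3. Assumed: test vs the other reference 3, each reference vs untreated 8, reference vs reference 3.
   - Pooled variance = (64 + 9 + 9 + 64 + 64 + 9)/6 = 36.5, SD 6.04.
   - Model SE at N=40 = 6.04/√40 = 0.955; true SE of test vs untreated = 8/√40 = 1.265.
   - A true null is rejected beyond 1.98 × 0.955/1.265 = 1.50 true SEs: about 13.5%. Simulation with estimated variance gives 13.8% two-sided, 6.8% in favour.
   - Apparent power for 3.5 vs no treatment is 90%; power for 2 vs a reference falls from 98% to 59%.
   - Holding 8, 3 and 3, reference vs untreated can lie between 5 and 11. Lowest pooled variance: (64 + 9 + 9 + 25 + 25 + 0)/6 = 22, SD 4.69, rejection rate 25%. Highest: (64 + 9 + 9 + 121 + 121 + 0)/6 = 54, SD 7.35, rate 7%.

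5. **Cost of an order.** The lead test fails with chance 1 − 0.770 = 23% at N=40 and 1 − 0.858 = 14% at N=50. With the step 4 SDs and separate paired tests, the lead test and both TEWL reference comparisons succeed together in 75% and 85%, whether both creams are required or Holm is used.

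**The case against.** The best counter-argument is that the plan already has a lead test. The sample-size text, the synopsis and Protocol 11.5 all point to TEWL versus no treatment, and on that reading nothing is inflated. The reference comparisons are called secondary in SAP 2.3, and SAP 7.5 treats secondary analyses as exploratory. This is also an early phase 2 study with every comparison prespecified. Most of this stands, and it is why the remedy is wording. It does not close the gap: SAP 7.1 lists the reference comparisons as primary, SAP 4.1 puts redness inside both hypotheses, and no text says which reading governs the claim.

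A reader might infer a false-positive rate of 37%, from 1 − 0.95⁹. The documents do not support that. It treats the tests as independent although they share sites and subjects, counts errors against the test cream as well as for it, and assumes any one result is enough.

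On the variance point, the SDs come from a similar earlier study, and the SD of 3 is given for one reference only. If the other reference had SD 8 against test cream, first reference and untreated, the pooled variance would be (5 × 64 + 9)/6 = 54.8 and the error about 7%. SAP 7.1 also allows alternatives if assumptions fail, and SAP 2.4 schedules assumption checks at blind review. That is a fair safeguard, but unequal variances are not named and no default is given.

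**Conclusion.** The gap is real and moderate: it should be closed, but it does not invalidate the design. The plan fixes nine primary tests and a level for each, but not the rule that links them to a superiority claim. The better-supported readings carry no inflation; the next gives about 4-7%, and the loosest about 10-18%, against 2.5%. The last two ranges depend on the assumed correlations and on tests of nominal size.

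It would go too far to say that the plan has no lead comparison, or that its error rate is 10-18%. It would also go too far to report 14% as the error rate of the TEWL versus no treatment test in this trial. That figure needs the assumed SDs and leaves out the Day 29 covariate, with 7-25% over other SDs compatible with 8, 3 and 3. What the documents do show is that SDs of about 8 and about 3 sit badly with one error variance.

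**What to change.** Before unblinding, state in SAP 7.5:

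- TEWL versus no treatment is the lead test, at full two-sided 5%, with success meaning a difference in favour of the test cream.
- The TEWL comparisons with the two reference creams are tested only if the lead test succeeds: either both are required (no adjustment), or Holm is used if either cream alone may support a claim.
- The redness comparisons are supportive, or enter at a stated later step that does not gate the TEWL reference comparisons. No redness SD is given, so the power of a redness gate cannot be calculated.

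Reconcile the status of the 2D erythema index between Protocol 11.2.1 and SAP 6.4, and record the change under Protocol 13.3. In SAP 7.1, state that each contrast uses its own standard error, from a paired within-subject contrast or a mixed model with unequal variances.

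The cost is text only: no change to visits, data or N. The drawback is that a failed lead test (about 23% at N=40, 14% at N=50) makes the later comparisons descriptive. Separate standard errors also lower the apparent power versus no treatment, from 90% in the pooled example to 77% at N=40. The Day 29 covariate may recover some of this: if it explained 0-30% of the variance of the difference (assumed), power would be 77-90% at N=40 and 86-95% at N=50.

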# 7.6 Missing and unusual data

Missing data will not be replaced. If appropriate the drop out rate will be calculated and analysed.

During data review (prior to data base lock and unblinding), readings that are incorrect, i.e. outside the equipment measurement range, will be removed. However, all readings that are possible, even if they are unusually low or high, will be kept in the analysis.

# 7.7 Interim Analysis:

No interim analyses are planned for this trial.

# 7.8 Data Monitoring Committee (DMC):

No DMCs are planned for this trial.

# 7.9 Changes From Protocol

An additional exploratory analysis has been proposed for the blind data review to investigate any impact of the location or adherence of the SLS patches on the observed data at day 31. This is due to investigators noting that the patches may not adhere so well in different locations along the forearm and also that the skin may react differently depending on distance from wrist/elbow.

# 8. List of Tables, Figures and Listings

# **Tables**

 
14.1.1 Disposition
 
14.1.2 Important PDs (Full Analysis Set)
 
14.1.3 Patients excluded from analysis populations (Full Analysis Set)
 
14.1.4 Demographic data (Full Analysis Set)
 

14.1.3 Patients excluded from analysis populations (Full Analysis Set)

14.1.4 Demographic data (Full Analysis Set)

14.1.4 Demographic data (Full Analysis Set)
14.1.5 Baseline eczema history (Full Analysis Set)
0 \
14.1.6 Medical History (Full Analysis Set)
14.1.7 Temperature and humidity during skin assessments
14.2.1 TEWL (g/m2h)  14.2.1 TEWL (g/m2h) next induction of skin imitation of the Association of the induction of the inductio
14.2.1.1 Change in TEWL (g/m2h) post-induction of skin irritation after 4 weeks of treatment (Day 31 – Day 29)
14.2.1.2 Analysis of change in TEWL post induction of skin irritation (day31-Day29)
14.2.1.3 Change in TEWL (g/m2h) after 4 weeks of treatment ( Day 29- Day1)
14.2.1.4 Analysis of change in TEWL following 4 weeks of treatment
14.2.2 Investigator visual scores for redness
14.2.2.1 Change in visual score for redness post-induction of skin irritation after 4
weeks of treatment (Day 31 – Day 29)
14.2.2.3 Analysis of change in visual score for redness post induction of skin
irritation (day31-Day29)
14.2.2.4 Analysis of visual score for redness at day 29.
14.2.3 Objective Erythema from 2D colour skin images
14.2.3.1 Change in Objective Erythema post-induction of skin irritation after 4
weeks of treatment (Day 31 – Day 29)
14.2.3.2 Analysis of change in Objective Erythema post induction of skin irritation
(day31-Day29)
14.2.3.3 Change in Objective Erythema after 2 and 4 weeks of treatment
14.2.3.4 Analysis of Objective Erythema from baseline to day 15 and day 29.
14.2.4 Objective Redness (Mexameter)
14.2.4.1 Change in objective skin redness (Mexameter) after 4 weeks treatment to
post-induction of skin irritation (Day 31 – Day 29)
14.2.4.2 Analysis of change in objective redness
14.2.5 Skin Capacitance measurements
14.2.5.1 Change in skin capacitance (Day 29 – Day 1)
14.2.5.2 Analysis of change in skin capacitance
14.2.6 Skin surface dryness (Sa (µm) 3D skin images) (Day 29 – Day 1)
14.2.6.1 Change in skin surface dryness, Sa (µm) (Day 29-Day1)
14.2.6.2 Analysis of change in dryness, Sa (µm)
14.2.7 Patient tolerability scores (VAS)
14.2.7.1 Analysis of patient tolerability scores (VAS)
14.2.8 Total Cream consumption
14.2.9. NMF
14.2.9.1 Analysis of NMF scores
14.2.10 Summary of FLG
14.3.1 Number of patients experiencing AEs
14.3.2 Adverse Events by system organ class and preferred term
14.3.x Adverse Events - further tables as appropriate
Listings

16.2.1	Discontinued patients
16.2.2	Protocol deviations
16.2.3	Patients excluded from analysis populations
16.2.4.1	Demographic data
16.2.4.2	Baseline eczema history
16.2.4.3	Medical history
16.2.4.4	Patient routine
16.2.5	Cream consumption
16.2.6.1	TEWL
16.2.6.2	Investigator visual scores for redness
16.2.6.3	Objective erythema
16.2.6.4	Objective Redness (Mexameter)
16.2.6.5	Skin Capacitance measurements
16.2.6.6	Skin surface dryness (3D skin images) (Day 29 – Day 1)
16.2.6.7	Patient tolerability scores (VAS)
16.2.6.8	Total Cream consumption
16.2.6.9	NMF
16.2.6.10	FLG
16.2.7	AEs

# Figures:

Figure 14.2.1.1	Change in TEWL (g.m2h) post induction of skin irritation (Day 31-Day 29)
Figure 14.2.1.2	Change in TEWL 9gm2h) after 4 weeks of treatment (Day29-Day1)
Figure 14.2.2.1	Change in visual score for redness post-induction of skin irritation (Day 31 –
	Day 29)
Figure 14.2.4.1	Change in objective skin redness (mexameter) (Day 31 – Day 29)
Figure 14.2.5.1	Change in skin capacitance (Day 29 – Day 1)
Figure 14.2.6.1	Change in skin surface dryness, Sa (µm) (Day 29-Day1)
Figure 14.2.9.1	NMF levels at Day 29
